11.4 Planned Interim Analyses

There are no planned interim analyses in this study.

11.4.1 Safety Review

There are no specific safety outcome measures in this study. Reported AEs will be reviewed after each challenge cohort. Unexpected or serious events judged to be related to the virus challenge will be reviewed with the ISM, the DSMB and DMID before the next cohort is challenged.

11.4.2 Immunogenicity or Efficacy Review

Immunogenicity or efficacy are not relevant to this study.

11.5 Analysis Plan

11.5.1 General Statistical Plan

General statistical support related to the primary outcome measure, and many of the parameters assessed under exploratory objectives will be provided by [name], MS (Pstat® Accredited Senior Biostatistician, Department of Public Health Sciences). Analyses performed by [name] will include, but are not limited to: (a) comparing infection rates resulting from primary challenge with RV-16 and re-challenge with RV-16 or RV-39, (b)

comparing RV-specific T-cell numbers before and after primary RV-16 challenge, (c) examining correlations between specific T-cell numbers and quantitative shedding as assessed by culture and qPCR as well as the time to virus shedding, (d) comparing clinical outcomes (e.g., cytokine response, and symptom scores) between primary RV challenge and RV re-challenge, and (e) examining correlations between RV specific T-cell numbers and clinical outcomes.

11.5.2 Primary Outcome Analyses (Correlation between the number of pre-existing RV-16 specific T-cells (15 wks.) and infection following re-challenge with RV-39 as assessed by virus shedding in nasal lavage)

Infection rates at primary challenge and the infection rates at secondary challenge will be analyzed by way of a binomial generalized estimating equation (GEE) model [37]. The GEE model response variable will be a binary indicator variable that will be assigned the value 1 if the volunteer is deemed infected on RV challenge and the value 0 will be assigned otherwise. The GEE model predictor variable will be 3 level classification variable. One level will differentiate the primary RV-16 challenge outcome data from the secondary RV challenge outcome data, a second level will identify the secondary RV-16 challenge outcome data, and the third level will identify the secondary RV-39 challenge outcome data. Since we expect that approximately 90% of the volunteers who undergo the primary RV-16 challenge will be eligible to undergo either RV-16 or RV-39 re-challenge, we cannot legitimately assume that the primary challenge infection status and re-challenge infection status of the volunteers who undergo re-challenge are statistically independent. To account for possible *intra-subject* measurement correlation, the components of the GEE model variance and covariance matrix will be estimated by the Huber and White sandwich estimator [38, 39].

With regard to hypothesis testing, the GEE version of the Wald test will be used to test whether the log-odds for infection is the same for the primary RV-16 challenge and the RV-16/RV-39 re-challenge. The Wald test will also be utilized to test whether the log-odds of infection is the same for the RV-16 and RV-39 re-challenges. For the primary challenge versus re-challenge comparisons, a 0.025 one-side decision rule will be utilized as the null hypothesis rejection criterion, while for the RV-39 re-challenge versus RV-16 re-challenge comparison, a two-sided 0.05 decision rule will be utilized as the null hypothesis rejection criterion. With regard to odds ratio confidence interval construction, the GEE version of Wald confidence interval will be utilized to estimate the lower and upper limits of the 95% confidence interval. The relationship between the number of pre-existing RV-16 specific T-cells (15 wks.) and infection following re-challenge with RV-39, as assessed by virus shedding in nasal lavage, will be quantitatively expressed in terms of the Pearson Product-Moment correlation coefficient if the bivariate normal assumption is deemed creditable based on the observed data, or quantitatively expressed in terms of the Spearman Rank correlation coefficient if the bivariate normal assumption is not supported by the observed data. In either case, the pivotal quantity for the null hypothesis test that the true correlation coefficient is equal to zero will be the Fishers z-statistic, and a two-side $p \leq 0.05$ decision rule will be utilized as the null hypothesis rejection criterion. Confidence interval construction for estimating the underlying correlation coefficient will be based on the Fishers z-transformation method [40].

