11.3 Sample Size Considerations

11.3.1 Sample Size Calculation Summary

The number of subjects enrolled for initial challenge with RV16 (80) is determined based on power analyses related to the primary outcome measure in Aim 2. In Aim 2, our sample size is designed to address the hypothesis that ***high frequencies of pre-existing RV-16-specific memory T cells directed against conserved epitopes protect against RV-39 infection.*** **Our primary objective is to test the relationship between the frequency of RV-16-specific memory T cells at 15 weeks and viral infection in response to re-challenge with RV-16 or RV-39.** In order to do this, we must first establish that there is a scientifically meaningful reduction in the RV infection rate for secondary versus primary RV challenge. A sample size of 35 volunteers per re-challenge will provide a two-sample test of equal proportions with 85% statistical power (with a one-sided $\alpha=0.025$ type I error rate) to detect a reduction of as small as 28% between the infection rate following primary challenge and the infection rate following secondary challenges.

If we have 35 volunteers per re-challenge, and if the underlying bivariate correlation between the frequency of RV-16-specific memory T cells at 15 weeks and viral infection in response to secondary challenge with RV-16 or RV-39 is at least 0.46 units in absolute magnitude - which if true, would be considered a scientifically meaningful association - we expect to have at least 0.80 statistical power to reject the null hypothesis that there is no correlation between the frequency of RV-16-specific memory T cells at 15 weeks and viral infection in response to secondary challenge with RV-16 or RV-39.

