11.3.2 Power Calculation Details

The “TWO SAMPLE FREQ” statement of the SAS version 9.4 (SAS Institute Inc., Cary, NC) “POWER Procedure” was used to conduct the first portion of the power analysis. As user input, the infection rates for the primary and secondary RV challenges were specified as 0.90 and 0.65, respectively. A zero difference in the infection rates of the primary and secondary RV challenges was specified as the null difference and the alternative difference was specified as a 0.25 unit reduction (i.e., $0.90 - 0.65$) in the secondary RV challenge infection rate compared to the primary challenge infection rate. In accordance with the alternative hypothesis “less than” direction, an $\alpha=0.025$ one-sided type I error rate was specified, and the group sample sizes were specified as $n=80$ for the primary RV challenge and $n=35$ for the secondary RV challenge. Based on this set of input parameters, a sample size of 35 volunteers per re-challenge should provide a statistical test with at least 85% power (with a one-sided $\alpha=0.025$ type I error rate) to detect a reduction of as small as 28% (i.e., $[(0.90-0.65)/0.90 \times 100\%]$) between the infection rate following primary challenge and the infection rate following secondary challenge.

The “ONE CORR” statement of the SAS version 9.4 “POWER PROCEDURE” was used to conduct the second portion of the power analysis. As user input, the null correlation was specified to be zero and the alternative correlation was specified to be 0.46. The test statistic was specified as the “Fishers z statistic”, and the two-sided type I error rate (α) was specified as $\alpha=0.05$. Based on this set of input variables, the power to detect a correlation of 0.46 in absolute magnitude is 0.81.

The rationale for the number of subjects screened is as follows:

- 750 volunteers will be screened for antibody to provide approximately 120 volunteers who are seronegative to both RV-16 and RV-39.
- Of the 120 resulting seronegative volunteers, approximately 96 will have a matched RV tetramer available for the T-cell studies.
- 80 eligible subjects (after review of other inclusion/exclusion criteria) will be challenged with RV-16, approximately 72 (90%) will be infected.
- 70 subjects (35 per virus) will be rechallenged with either RV-16 or RV-39.

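### Infection rates are compared only on the log-odds scale: no interval is planned for the rate reduction that sized the study, and no rule covers a re-challenge arm with 0% or 100% infected

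*Combined protocol and SAP*

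**What the plan says.** Section 11.3.1 makes the rate comparison a precondition for the T-cell correlation: "we must first establish that there is a scientifically meaningful reduction in the RV infection rate for secondary versus primary RV challenge". It is sized as a test of proportions: "A sample size of 35 volunteers per re-challenge will provide a two-sample test of equal proportions with 85% statistical power". Section 11.3.2 gives the inputs: "the infection rates for the primary and secondary RV challenges were specified as 0.90 and 0.65, respectively", 80 primary and 35 re-challenged volunteers, and a one-sided error rate of 0.025. The effect is described on the rate scale, with power "to detect a reduction of as small as 28" per cent.

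Section 11.5.2 analyses infection with a binomial GEE, a three-level challenge factor and a sandwich variance. The test is on log-odds: "the GEE version of the Wald test will be used to test whether the log-odds for infection is the same". The decision rule matches the sizing: "For the primary challenge versus re-challenge comparisons, a 0.025 one-side decision rule will be utilized as the null hypothesis rejection criterion". The RV-16 versus RV-39 re-challenge contrast uses the same Wald test at two-sided 0.05. For odds ratios, "the GEE version of Wald confidence interval will be utilized to estimate the lower and upper limits of the 95% confidence interval". Section 11.5.3 repeats all of this.

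Section 11.5.1(a) lists a comparison of infection rates but gives no further method. Nowhere is there a risk difference, a risk ratio, a working correlation, or a fallback for an arm in which nobody or everybody is infected.

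**The concern.** There are two gaps. First, the target is a reduction in rate, but the only planned estimate with an interval is an odds ratio. With rates between 65% and 90%, an odds ratio cannot be read against a 28% reduction, so the final report could reject the null without saying, with an interval, whether the fall was as large as the study was built to detect.

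Second, a logit coefficient for an arm with no infected or no uninfected volunteers has no finite estimate. The sandwich variance for that arm is then built from residuals that are all close to zero, so the standard error need not warn the analyst. With 35 volunteers per arm and no fallback, the analyst would have to choose a method after seeing the data. A literal application of the rule could declare a difference where there is none.

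**Working it through.** **Inputs.** Rates 0.90 and 0.65, n = 80 and 35, one-sided alpha 0.025 (11.3.2); logit GEE, three levels, sandwich variance, Wald test (11.5.2). Re-challenge rates other than 0.65 are assumptions, because the documents give no rate specific to homologous re-challenge. Steps 1, 2 and 4 treat groups as independent, as the plan's own power calculation does.

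**1. The plan's figure.** Pooled rate = (80 × 0.90 + 35 × 0.65)/115 = 94.75/115 = 0.824. Null SE = √[0.824 × 0.176 × (1/80 + 1/35)] = 0.0772. Alternative SE = √[0.09/80 + 0.2275/35] = 0.0873. Power = Φ[(0.25 − 1.96 × 0.0772)/0.0873] = Φ(1.130) = 0.871, which meets the stated minimum of 85%. The relative reduction is 0.25/0.90 = 27.8%, the stated 28%.

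**2. The same alternative on the log-odds scale.** Difference = ln(0.90/0.10) − ln(0.65/0.35) = 2.197 − 0.619 = 1.578. SE = √[1/(80 × 0.09) + 1/(35 × 0.2275)] = 0.514. Power = Φ(1.578/0.514 − 1.96) = Φ(1.109) = 0.866. Exact enumeration gives 0.888 for the proportions test and 0.876 for the log-odds Wald test.

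**3. What the odds ratio conveys.** Odds ratio = 1.857/9 = 0.206; rate ratio = 0.65/0.90 = 0.72. The same 28% relative fall from a 75% baseline (0.75 to 0.542) has an odds ratio of 0.39. One rate reduction therefore corresponds to different odds ratios, depending on the baseline.

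**4. What a rate-scale report would look like.** For 72/80 versus 23/35 the difference is 0.900 − 0.657 = 0.243, with Newcombe 95% interval 0.084 to 0.415 (illustrative, pairing ignored).

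**5. Empty cells.** The planned model was fitted in statsmodels with sandwich variance, pairing infections at random within volunteers.

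| Primary, RV-16, RV-39 | Working correlation | Result |
|---|---|---|
| 72/80, 1/35, 23/35 | independence | RV-16 log OR −5.7, SE about 1.1: usable |
| 72/80, 0/35, 23/35 | independence | RV-16 log OR −27.8, SE 0.39 to 0.43 depending on pairing |
| 72/80, 0/35, 23/35 | exchangeable | NaN, or estimates in the hundreds or thousands (such as −1996) with SE 0 |
| 72/80, 35/35, 34/35 | independence | RV-16 versus RV-39 contrast 22.04, SE 1.03, z = 21.4 |
| 72/80, 35/35, 34/35 | exchangeable | NaN, or an arbitrary large value |

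Fisher's exact p for 35/35 versus 34/35 is 1.0. For 72/80 versus 0/35, rate-scale methods remain defined: difference 0.900, Newcombe 0.770 to 0.948, score 0.814 to 0.949 (pairing again ignored).

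**6. How often.** P(0/35) = (1 − q)^35.

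| True re-challenge rate q | P(0/35) |
|---|---|
| 0.65 (planned) | 1 × 10⁻¹⁶ |
| 0.20 | 0.04% |
| 0.10 | 2.5% |
| 0.05 | 17% |
| 0.02 | 49% |

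At the other end, P(35/35) = q^35, which is 3 × 10⁻⁷ at 0.65 and 0.025 at 0.90. If both arms have a true rate of 0.90, the chance that exactly one is 35/35 is 2 × 0.025 × (1 − 0.025) = 4.9%.

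**The case against.** Equal log-odds and equal rates are the same null hypothesis, tested in the same direction at the same one-sided 0.025, and step 2 shows almost no loss of power. With a single three-level factor and independence working correlation, the fitted rates equal the observed proportions, so the reduction can be read off directly. The named primary outcome is the T-cell correlation, not this comparison. All of this stands. It reduces the scale point to a missing interval.

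On empty cells, a reader might infer that 0/35 is the expected result because homologous re-challenge serves as a positive control. The documents do not support that. Section 4.1 sets the two re-challenges side by side, and 11.3.2 uses one rate, 0.65, for re-challenge. Section 5.2.1 does not require infection at first challenge, and 11.3.2 expects 72 of 80 to be infected, so some re-challenged volunteers may never have had RV-16.

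It can also be said that a failed fit is usually obvious: NaN, or an odds ratio near 10⁻¹², would be noticed. That is often true, but the outcome depends on a working correlation that the plan does not name. Noticing the failure also does not say what to do instead. A z of 21.4 with a standard error near 1 is not self-evidently a failure.

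**Conclusion.** The point holds in a limited form. The planned test is valid and adequately powered while every cell is non-empty; it would be wrong to infer that the log-odds test addresses a different hypothesis or undermines the sample size. What is missing is a pre-specified estimate and interval on the rate scale (0.25, or 28%), for which an odds ratio of 0.21 is no substitute.

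Separately, the stated Wald rule gives an invalid answer when a re-challenge arm is 0% or 100% infected. The probability is negligible at the planned 0.65. It becomes material only under assumptions outside the plan's sizing: a true homologous rate of about 5% or lower (17% chance of 0/35 at 5%), or no protection in either arm (4.9% chance that exactly one arm is 35/35 at 0.90). The fitted values are specific to the package and pairing used; the absence of a finite logit estimate is not. This should be fixed, but it does not threaten the design.

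**What to change.** In 11.5.2 and 11.5.3:

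- Add the risk difference and risk ratio, each with a 95% interval, for every infection-rate comparison. When all cells are non-empty, standardise them from the logit GEE and use an interval that allows for within-volunteer pairing, for example a bootstrap that resamples volunteers. The odds ratio may stay as a supplement.
- State that if any cell is 0% or 100%, the Wald test and interval are replaced by an exact or score test and a score-type interval. Between the randomised re-challenge arms, use an exact unconditional or Fisher test. For primary versus re-challenge, use exact McNemar among re-challenged volunteers, noting that it omits those not re-challenged (about 10 of 80 on the planned numbers).
- Do not use an identity-link GEE for empty cells. Fitted to 72/80, 0/35 and 23/35, it either failed to converge or gave a falsely tight interval (roughly 0.83 to 0.97), because the empty arm contributes almost no variance.
- Name the working correlation.

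Section 15.4 places the analysis after all clinical interventions, so the wording should be fixed before infection results are seen. The cost is SAP text, slightly more analysis work, and a slightly conservative exact test in the rare empty-cell case. Sample size, visits and conduct do not change.

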The current study will use major histocompatibility complex class II (MHCII) tetramers that display conserved RV-16 peptide epitopes to identify and track circulating RV-specific CD4⁺ T cells in subjects who receive sequential RV challenges with RV-16 and RV-39 (Fig. 1 and Table I). This will allow us to interrogate adaptive immunity to heterotypic RV strains. Preliminary work performed under a separate pilot study established the feasibility of this approach. In that study, tetramer-guided epitope mapping [16] was used to develop two DRB1*0401 tetramers that displayed conserved RV-39 epitopes (one each for capsid protein VP1 and VP2). The pilot study included 16 healthy DRB1*0401+ subjects (ages 18-60 years old) who participated in a RV-39 experimental challenge study. All subjects had no history of allergies and were seronegative for RV-39 (serum neutralizing antibody titer $\leq 1:4$) (see enrollment, Fig. 2). Challenge with RV-39 was administered intranasally (2 doses per nostril of a 0.25 mL solution containing 100 TCID₅₀/mL). RV-39 antibody titer was re-tested immediately before challenge (day 0) and during convalescence (day 21). Those subjects experiencing ≥ 4 -fold increase in RV-39 serum neutralizing antibody titer, or at least one RV-39 positive nasal culture, were considered infected. Peripheral blood mononuclear cell (PBMCs) were isolated from DRB1*0401+ subjects before RV challenge (days -28 and 0), and during acute (day 5) and convalescent (day 21) phases (model, Fig. 2). Samples were frozen and then thawed for analysis upon study completion. Tetramer staining and flow cytometry analysis was performed using established methods. A control tetramer containing an irrelevant peptide (GAD555-567) provided a negative control [23-25, 27, 28].

[figure not shown]
[figure not shown]

Fig. 2. Experimental RV-39 challenge study. Enrollment of DRB1*0401+ subjects and RV-39 challenge study design. Arrows in the model denote PBMC sampling time points.

Of the 16 DRB1*0401+ subjects enrolled, 12 were infected and 4 were uninfected. In *post hoc* tests, 3 subjects had evidence of recent RV exposure based on positive serum neutralizing

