9.2.1 Historical performance of the challenge model

The experimental RV challenge model is a well-established model that has been used for the study of the pathogenesis and treatment of rhinovirus infections since the 1960s. There have been a number of variations on the model but the proposed procedures and evaluations in this protocol (described in section 8.2 above) and have been used by the PI for 35 years. Under these conditions, the expected infection rate for volunteers in the study is 85-90%. Mean symptom scores for the RV39 used in the study have typically been in the range of 14-18 with standard deviations of ± 13 . The mean total symptom scores for the RV16 was 20 ± 10 in the initial evaluation of the challenge pool.

The investigators are not aware of any previous rhinovirus challenge study that was discontinued because of unexpected risk to the volunteers in the study. In light of this experience, it is unlikely that events that would require stopping the study would occur.

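### The one-sided test of RV-39 re-challenge against primary RV-16 challenge mixes serotype with prior immunity, so it cannot by itself show cross-protection

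*Combined protocol and SAP*

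**What the plan says.** All volunteers are challenged with RV-16 and, about 15 weeks later, randomized to RV-16 or RV-39 (4.1, 5.4.1). The infection model in 11.5.2 has three levels: primary RV-16, secondary RV-16 and secondary RV-39. There is no first-challenge RV-39 level. The Wald test is used to "test whether the log-odds for infection is the same for the primary RV-16 challenge and the RV-16/RV-39 re-challenge", and for the comparisons of primary challenge with re-challenge "a 0.025 one-side decision rule will be utilized as the null hypothesis rejection criterion". The text does not say whether the two re-challenge groups are tested separately or pooled. Section 11.5.3 repeats the same wording.

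Section 11.3.1 gives this test a leading role: before the T-cell question is addressed, "we must first establish that there is a scientifically meaningful reduction in the RV infection rate for secondary versus primary RV challenge". In 11.3.2, "the infection rates for the primary and secondary RV challenges were specified as 0.90 and 0.65, respectively" and "the group sample sizes were specified as $n=80$ for the primary RV challenge and $n=35$ for the secondary RV challenge". One pair of rates serves both viruses.

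On infectivity, section 2.2 gives 80-90% for challenged volunteers. Section 9.2.1 says that "the expected infection rate for volunteers in the study is 85-90" percent. Neither figure is split by serotype. The only first-challenge infection count specific to RV-39 is in the background account of the pilot study: "Of the 16 DRB1*0401+ subjects enrolled, 12 were infected and 4 were uninfected". Section 9.2.2.2 checks the infection rate only at the first RV-16 challenge and expects a changed rate at re-challenge to reflect the design rather than the model.

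**The concern.** For RV-16 re-challenge, the reference is the same virus in the same people before immunity, so a fall in infection can be attributed to prior exposure, subject to season. For RV-39, the reference is a different virus. The difference in log-odds is then the sum of two terms: naive RV-39 against naive RV-16, and immune against naive for RV-39. Only the second is cross-protection, and the design cannot separate the two. The sandwich variance deals with repeated measures on a subject, not with this.

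The randomized comparison of RV-16 with RV-39 at re-challenge does not resolve it, because that comparison mixes natural infectivity with homologous versus heterologous immunity.

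At stake is the interpretation of a significant RV-39 result. Section 2.2 states the aim as proof of concept for cross-protection, 11.3.1 puts the reduction first, and 9.2.2.2 leans toward attributing changes to the design. Read together, they invite the conclusion that a lower RV-39 rate means protection. The 0.025 error rate does not apply to that conclusion.

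**Working it through.** **Inputs from the plan.** Primary rate 0.90, n = 80; re-challenge rate 0.65, n = 35; one-sided 0.025, z = 1.96 (11.3.2, 11.5.2). Model infection rate 80-90% (2.2) or 85-90% (9.2.1). RV-39 pilot 12/16 (background).

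**Assumed.** Naive RV-39 rates of 0.90, 0.85, 0.80 and 0.75. The documents do not establish any of them.

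**1. The plan's own figure.** The plan states that "a sample size of 35 volunteers per re-challenge should provide a statistical test with at least 85% power".
- Pooled rate = (80 × 0.90 + 35 × 0.65)/115 = 0.824.
- Null SE = √[0.824 × 0.176 × (1/80 + 1/35)] = 0.0772.
- Alternative SE = √[0.90 × 0.10/80 + 0.65 × 0.35/35] = 0.0873.
- Power = Φ[(0.25 − 1.96 × 0.0772)/0.0873] = Φ(1.13) = 87.1%.

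The stated figure is reproduced.

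**2. Rejection with no cross-protection.** Set the RV-39 re-challenge rate equal to its naive rate q and hold primary RV-16 at 0.90. By normal approximation at q = 0.80:
- Log-odds difference = ln 9 − ln 4 = 0.811.
- SE = √(1/72 + 1/8 + 1/28 + 1/7) = 0.563.
- Rejection = Φ(0.811/0.563 − 1.96) = Φ(−0.52) ≈ 30%.

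Exact enumeration of two independent binomials, and simulation of the three-level GEE contrast with a subject-level sandwich variance (20,000 runs per setting, latent within-subject correlation 0, 0.3 and 0.6), give:

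| Naive RV-39 rate q | Odds ratio with no protection | Log-odds Wald, exact | Pooled chi-square, exact | GEE simulation |
|---|---|---|---|---|
| 0.90 | 1.00 | 2.5% | 3.1% | 2.4-3.0% |
| 0.85 | 0.63 | 12.1% | 13.3% | 12-15% |
| 0.80 | 0.44 | 30.5% | 32.4% | 30-38% |
| 0.75 | 0.33 | 53.3% | 55.6% | 53-62% |

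The odds ratio is [q/(1 − q)]/9. Allowing for the overlap of subjects does not lower the figures materially.

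**3. Effect on the estimate.** If RV-39 re-challenge infection is 0.65, the apparent drop is 0.90 − 0.65 = 25 points. The part due to protection is q − 0.65: 20 points at q = 0.85, 15 at 0.80 and 10 at 0.75.

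**4. The other direction.** Suppose the naive rates are 0.80 for RV-16 and 0.90 for RV-39, both inside the range in section 2.2, and prior infection lowers RV-39 infection by 10 points. The contrast then compares 0.80 with 0.90 − 0.10 = 0.80, and real protection disappears.

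**5. If the re-challenge groups are pooled (70 against 80).**
- No protection from either virus: rejection is about 15% at q = 0.80 and 27% at q = 0.75.
- RV-16 re-challenge at 0.65 and RV-39 at an unprotected 0.90: the pooled rate is (0.65 + 0.90)/2 = 0.775, and rejection is about 55%. Homologous protection alone drives that result.

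**6. Weight of the pilot.** 12/16 = 75%, exact 95% CI 48-93%. The probability of 12 or fewer infected out of 16 is about 21% at a true rate of 85% and about 7% at 90%.

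**The case against.** A reader might infer from the pilot that RV-39 is the less infective virus, and that a false claim of cross-protection is therefore likely. The documents do not support that. The pilot's interval includes 90%. The pilot also used a titer cut-off of 1:4 rather than 1:2, enrolled ages 18-60 and a single HLA type, and had three subjects with evidence of recent rhinovirus exposure. Section 2.2 describes both strains as having known infectivity and gives one range for the model. Section 6.2.1 gives both pools the same stock titer, target range, volume and route, so no inoculum difference between the viruses is documented. Within the 85-90% of 9.2.1, the false-reduction rate is 2.5% to about 13% (up to 15% in the GEE simulation).

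It is also fair to say that the primary outcome is the correlation of T-cell number with infection (3.2.1, 11.2.3), which is computed within the re-challenge group and does not use this contrast. The requirement to show a reduction first appears in the sample-size rationale, and 11.5.2 does not make it a formal gate. No sentence states that rejection means cross-protection. For the literal null of equal log-odds, the 0.025 level holds approximately.

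All of this stands, and it limits the strength of the point. It does not make the RV-39 contrast interpretable as protection: equal naive infectivity remains an assumption that the design cannot test.

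**Conclusion.** The RV-39 against primary RV-16 test confounds serotype with prior immunity. With no cross-protection and a primary RV-16 rate of 90%, the chance of a significant reduction is about 12-13% at a naive RV-39 rate of 85% and about 31-32% at 80% (12-15% and 30-38% under the simulated GEE). Both are assumed scenarios inside the protocol's own 80-90% range; the second pairs the bottom of that range for RV-39 with the top for RV-16. The 53-56% at a naive rate of 75% is a worst case resting on a small, differently selected pilot, not an expectation. The direction of any bias is unknown.

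The stronger reading, that the trial's primary result is invalid, does not follow: the T-cell/infection correlation within the RV-39 arm is not biased by this contrast. The matter should be fixed before analysis, but it does not undermine the primary outcome.

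**What to change.** In 11.3.1 and 11.5.2, and in the repeated text of 11.5.3:

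1. Define the comparison of primary challenge with re-challenge separately for each virus, not pooled.
2. Keep the one-sided 0.025 reduction test as evidence of protection only for RV-16 re-challenge against RV-16 primary. Note that first challenges are in the fall and second challenges in winter/spring (5.1), so season affects that contrast too.
3. Report RV-39 re-challenge against primary RV-16 descriptively, as an estimate with a two-sided 95% confidence interval, and state that it mixes serotype with prior immunity and may be biased in either direction.
4. Remove the requirement to show a reduction first for RV-39. State that the heterologous conclusion rests on the within-arm T-cell/infection association already named as the primary outcome.

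The site's earlier first-challenge RV-39 infection rate could be added as supportive context if data from the same pool, with the same infection definition, exist. The documents do not show that they do, and a historical comparison brings its own differences in period and selection.

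The cost is wording and a more modest RV-39 claim. No extra subjects, visits or assays are needed.
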